6.5 Concomitant Therapy

Throughout the study, investigators may prescribe any concomitant medications or treatments deemed necessary to provide adequate supportive care except for those listed in Section 6.8.

The use of prescribed therapies (ie, bisphosphonate) will be allowed to manage adverse event (ie, hypercalcemia), if deemed necessary by the investigator.

Concomitant therapies are to be collected from informed consent through the end of study. Collect therapy name, indication, dose, unit, frequency, and route, start date, and stop date. Concomitant medications will not be collected after the end of study (EOS) visit for any subjects with additional safety follow-up.

Prior medication (medication taken 24 months prior to subject enrolling on study) will also be recorded on the concomitant eCRF.

6.6 Alcohol, Tobacco, and Drug Substances of Abuse Restrictions Subjects are not permitted to consume any alcohol within 24 hours prior to a study visit, including screening.

Subjects are not permitted to use nicotine or tobacco containing products or drug substances of abuse throughout the screening period and for the duration of the study.

6.7 Product Complaints

A product complaint is any written, electronic or oral communication that alleges deficiencies related to the identity, quality, durability, reliability, safety, effectiveness, or performance of a drug, **combination product**, or device after it is released for distribution to market or clinic by either (1) Amgen or (2) distributors **or** partners for whom Amgen manufactures the material. **This includes all components distributed with the drug, such as packaging drug containers, delivery systems, labeling, and inserts.**

Any product complaint associated with an investigational product supplied by Amgen are to be reported.

6.8 Excluded Treatments and/or Procedures During Study Period

All medications listed in the exclusion criteria, shown in the table below, or any other medication that is known or suspected to have activity on bone metabolism (except calcium and vitamin D) will not be allowed during the study.

aluminum	calcium chelators	parathyroid hormone (or a derivative)				
anabolic steroids	chemotherapeutics					
androgens ^a	chronic heparin use	progestins, when used as monotherapy				
anticonvulsants (gabapentin	(> / days)	prolonged alucocorticoid				
and benzodiazepines are	cinacalcet	therapy at a prednisone				
allowed)	blood citrated products	equivalent dose of				
any investigational agents other than study drug	fluoride	≥ 5.0 mg/day (tapering glucocorticoid courses of				
aromatase inhibitors	gonadotropin-releasing hormone agonists	\leq 1 month duration are				
biologics (except for insulins and vaccines)	growth hormone (unless	inhaled or topical glucocorticoids are permitted)				
bisphosphonate ^b	prior to screening)	protease inhibitors				
calcitonin	immunosuppressants	strontium				
	lithium	tibolone				

Table 4. List of Proscribed Therapies

^a Except subjects who are receiving testosterone therapy for physiologic replacement in the setting of documented hormonal deficiency

^b Will be allowed to manage adverse event (ie, hypercalcemia), if deemed necessary by the investigator

6.9 Contraceptive Requirements

Pregnant or breastfeeding females and females planning to become pregnant should not participate in this study. Females of reproductive potential, must use an acceptable method of highly effective birth control while on study through day 169 (for subjects who remain on study through completion or for 3 months after the last dose of study drug (for subject who withdraw prior to end of study).

A female is considered fertile following menarche and until becoming postmenopausal unless permanently sterile. Permanent sterilization methods include hysterectomy, bilateral salpingectomy, and bilateral oophorectomy.

Females are considered of reproductive potential if they have had menarche. Female subjects who have had menarche and those that experience menarche whiles on study will need to have pregnancy testing.

Female subjects of reproductive potential must agree to use highly effective methods of contraception (as described in the table below) and to continue this practice while on study through day 169 for subjects who remain on study through completion) or for 3 months after the last dose of investigational product (for subjects who withdraw prior to end of study).

Table 5. Acceptable Contraceptive Methods (Highly Effective) for Female Subjects

- Combined (estrogen and progestogen) hormonal contraception associated with inhibition of ovulation (oral, injections, intravaginal, or transdermal)
- Progesterone-only hormonal contraception associated with inhibition of ovulation (oral, injectable, or implantable)
- Intrauterine device
- Intrauterine hormonal-releasing system
- Bilateral tubal ligation/occlusion
- Vasectomized partner (provided that partner is the sole sexual partner of the female subject and that the vasectomized partner has received medical assessment of the surgical success)
- Sexual abstinence (defined as refraining from heterosexual intercourse during the entire period of risk associated with the study treatments).

If a female subject is suspected of being pregnant, the investigational product must be stopped immediately and may not be resumed until absence of pregnancy has been medically confirmed.

If a pregnancy occurs in a female partner of a male subject, while the subject is in the study, report the pregnancy to Amgen as specified below. In addition to reporting pregnancy during the study, investigators should monitor for pregnancies that occur through 3 months after the last dose with investigational product.

The pregnancy should be reported to Amgen Global Patient Safety **immediately and no later than** 24 hours of the investigator's knowledge of the event of a pregnancy. Report a pregnancy on the Pregnancy Notification Worksheet (Appendix C). Amgen Global Patient Safety will seek to follow the pregnant woman throughout her pregnancy and her baby up to 12 months after birth.

6.9.1 Unacceptable Methods of Birth Control for Female Subjects

Birth control methods that are considered unacceptable in clinical trials include: periodic abstinence (calendar, sympto-thermal, post-ovulation methods), withdrawal (coitus interruptus), spermicides only, and lactational amenorrhea method.

Female subjects of reproductive potential must receive pregnancy prevention counseling and be advised of the risk to fetus if they become pregnant during the study through day 169 (for subjects who remain on study through completion) or for 3 months after the last dose of investigational product (for subjects who withdraw prior to end of study).

6.9.2 Male Participants

Male participants are not required to use birth control during treatment with romosozumab.

- 7. STUDY PROCEDURES
- 7.1 Schedule of Assessments

Activity ^a	Screening	Treatment								Follow-up	EOS ^j			
Study Day	-35 to -1													
Time (in hours) ^b														
Visit Windows				±2 days	± 3 (days		±3 days	±3 days	±2 days	± 3 d	ays	± 7 days	6
General Assessments														
Informed Consent	Х													
Medical History	Х													
Physical Examination	Х	Х							Х			Х		Х
Facial Nerve (Cranial Nerve VII) Examination		Х							х			х		х
Vital Signs (HR, RR, TEMP)	Х	Х				Х			Х	Х	Х	Х	Х	Х
Weight	Х	Х				Х			Х					Х
Height	Х													Х
12-lead ECG	Х			Х		Х								Х
Echocardiogram ⁱ	Х													
Concomitant medications														
Adverse Event Recording		<												
Serious Adverse Event	<													,
Recording														
Central Laboratory Assessn	nents													
Clinical Chemistry with calcium, phosphorous, and magnesium levels	х	х		x		x			x	x		х	х	х
25(OH) Vitamin D Level	Х													
iPTH	Х	X		Х		X			Х			Х	Х	Х
Clinical Hematology	X	Х				Х			Х			Х		Х
HIV, HBcAb, HBsAg, and HepCAb	х													

Table 6. Schedule of Assessments

Page 1 of 2

Activity ^a	Screening						Tr	eatment						Follow- up	EOS
Study Day	-35 to -1	-													
Time (in hours) ^b															
Visit Windows				±2 days	± 3 (days		± 3 days	± 3 days		±2 days	± 3 (days	±7 da	iys
Local Laboratory Assessme	ents														
Pregnancy Test (Serum at screening, Urine dipstick method all other timepoints) ^c	х	х				х			x						х
Alcohol and drug testing ^d	Х														
Imaging Assessments															
DXA (AP lumbar spine)	Х												х		X
Dosing															
Dispensation of calcium and vit D			Х				Х			Х			х	Х	
n															
Pharmacokinetic and Other	Blood Sampl	es													
Serum PK		Х		Х	Х	Х			Х		Х	Х	Х	Х	Х
Bone Turnover Markers (sCTX and P1NP) ^e		Х		Х	Х	Х			Х		х	х	х	Х	Х
Antiromosozumab Antibody		X			Х	Х							X		х
Telephone Safety Assessm	ents														-
Telephone Safety Assessment ^g								Х							

Table 6. Schedule of Assessments

ECG = echocardiogram; EOS = end of study; HbsAg = hepatitis B surface antigen; HBcAb = hepatitis B core antibody; HepCAb = hepatitis C antibody; iPTH = intact parathyroid hormone; HIV = human immunodeficiency virus; HR = heart rate; P1NP = procollagen type 1 N-terminal propeptide; PK = pharmacokinetics; sCTX = serum type I collagen C-telopeptide; RR = respiratory rate; TEMP = temperature

^a The investigator may utilize investigator's staff or a qualified home healthcare service provider to provide such services at the subject's home as appropriate per institutional policies, local law and regulations, and in accordance with the study laboratory manual. Home visits can be performed for visit days 8, 15, 64, 71, and 113.

^b Relative to study drug administration on day 1

^c Pregnancy test will be performed for female subjects that have had menarche and for those that experience menarche while they are on the study. Screening pregnancy test will use serum samples, but all other pregnancy assessment will be done using urine samples.

^d At PI discretion according to local guidance.

esCTX and P1NP should be taken approximately the same time (+ 1 hour) of day 1 collection time.

⁹ PI or designee should perform telephone safety assessment on day 43 (± 3 days), the assessment should include recording any adverse or serious adverse event and any concomitant medications.

^h Injection site reactions (ISR) should be evaluated at every visit, approximately 20 to 30 minutes after administration of investigational product. Confirmed ISR should be appropriately reported as adverse events.

ⁱ Echocardiogram will be performed only at screening if subject does not have prior echocardiogram performed in the last 6 months.

^j If subject discontinues from study, the EOS visit will be the same as the follow-up visit. After end of study, serious adverse events, regardless of causality, will be reported to Amgen. Please refer to Section 9.2.3 for additional details.

7.2 General Study Procedures

Study tests and procedures will be performed only after written informed consent and subject assent (as applicable by local law) is obtained. During the study, every effort should be made to conduct study procedures as described in the Schedule of Assessments (Table 6). The investigator may utilize investigator's staff or a qualified home healthcare service provider to provide such services at the subject's home as appropriate per institutional policies, local law and regulations, and in accordance with the study lab manual.

Any missed visits, tests not done, and examinations not conducted must be reported as such on the eCRFs.

In the event that multiple procedures are required to be conducted at the same time, ECG and vital sign assessments should be performed before blood samples are drawn.

On-study bone turnover markers (BTM: sCTX and P1NP) samples should be collected approximately at the same time (\pm 1 hour) of day 1 collection time.

All blood samples should be collected at the same time at each visit.

Blood draws and safety assessments on dosing day should be performed before IP administration.

Additional procedures deemed necessary as part of standard of care or as required by local laws and regulations may be performed at the Investigator's discretion.

Acceptable windows for visits and PK and BTM sample collections:

- \pm 2 days for days 8 and 64
- \pm 3 days for days 15, 29, 57, 71, and 85
- \pm 7 days for days 113 and 169/EOS

Laboratory Assessments

For a complete listing of laboratory test panels and analytes, please refer to Section 7.4.12.

It is the responsibility of the investigator to ensure that all procedures are performed according to the protocol.

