2.2.2 Pharmacokinetics

Pharmacokinetic data are available from 9 single-dose phase 1 studies, 3 multiple-dose phase 1 studies, 2 multiple-dose phase 2 studies, and 3 phase 3 studies in adult

populations. Overall, the PK properties of romosozumab have been well characterized and are similar to that of other IgG monoclonal antibodies.

Romosozumab exhibits nonlinear PK consistent with target-mediated drug disposition. Elimination of romosozumab likely occurs via 2 mechanisms: nonspecific catabolism (as for other IgGs) and saturable degradation of the romosozumab-sclerostin complex. The kidney and liver are not routes of IgG elimination, as IgG antibodies are too large to be filtered by the glomerulus, and cytochrome P450-mediated metabolism and biliary secretion do not play a role. No demographic or physical characteristic, as well as BMD status or prior treatment with alendronate, has been found to warrant an adjustment in dose.

The PK of romosozumab was evaluated in healthy subjects following administration of a range of single SC doses. Generally, Cmax was observed within the first week after administration. Serum romosozumab concentrations declined with a mean half-life of approximately 11 to 18 days during the beta (plateau) phase and 6 to 7 days during the gamma (terminal) phase. The bioavailability of romosozumab was estimated to be 50% to 70% after SC administration of to mg/kg. Following administration of SC doses at mg/kg for a ccumulation based on mean C_{max} and every AUC values following 3 doses was 20% to 36% more than exposure after the first dose. The mean effective t_{1/2} was 12.8 days after 3 doses of mg/kg. Approximately linear PK was observed when comparing C_{max} and AUC values following and mg/kg When multiple SC doses of romosozumab 70, 140, or 210 mg QM were administered to women with PMO or low BMD, steady state was generally reached by month 3 with minimal accumulation (< 2 fold) following multiple doses and approximately dose-proportional increase in PK exposure was observed in the dose range of 140 mg to 210 mg.

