7.4.13.3 Serum PK and Bone Turnover Markers - sCTX and P1NP

All blood samples will be obtained by venipuncture before IP administration. The average volume of blood drawn per visit will be approximately 5 mL.

Blood will be obtained at the time points outlined in the Schedule of Assessments (Table 6). The date and time of blood collection will be recorded in the subjects' medical records. Only samples collected from subjects who received romosozumab are planned to be analyzed for romosozumab concentrations.

Serum PK samples will be collected at days 1, 8, 15, 29, 57, 64, 71, 85, 113, and 169/EOS.

Bone turnover marker samples will be collected at days 1, 8, 15, 29, 57, 64, 71, 85, 113, and 169/EOS.

All blood samples will be processed and sent to the central laboratory. The central laboratory will be responsible for completing assays and shipping samples to Amgen for performance of other assays. The central laboratory will be responsible for all serum chemistry, vitamin D, calcium, phosphorous, magnesium, hematology, sCTX, and P1NP, as well as serology assessments. The central laboratory will provide a study manual that outlines handling, labeling, and shipping procedures for all serum samples.

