10.4.2 Primary Endpoint(s)

Serum romosozumab concentrations will be determined using a validated assay. Individual serum concentration-time plots for romosozumab will be presented for each subject as well as mean concentration-time plots for each dose cohort. PK parameters will be estimated using either compartmental (eg, PK modelling) or non-compartmental methods. Actual dosing and sampling times will be used for calculation of PK parameters. Summary statistics will be generated for each PK parameter for each dose cohort.

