5.2 Study Points of Reference

Baseline

The baseline measurement is defined as the last measurement prior to the first dose of IP. If the measurement is taken on the same day as the first dose and the exact measurement time relative to the first dose is unknown, it will be assumed to have been taken prior to the first dose of IP. If a subject does not receive IP, baseline is the closest recorded measurement on or prior to the enrollment date.

Note: If baseline result from DXA assessment is not available, the results assessed on or before Study Day 14 will be considered baseline.

Study Day 1

Day 1 is defined as the first day that investigational product is administered to the subject. The day before Day 1 is referenced as Day -1.

Study Day

Post day of dose: study day= (study date - date of study Day 1) +1

Pre day of dose: study day= (study date – date of study Day 1)

The day prior to the first investigational product dosing is Day -1 while the day of the first investigational product dose is Day 1.

Analysis Visit

To allow for variations in scheduling study visits, the analysis visit windows defined in Appendix A will be used to assign evaluations to the most appropriate nominal visit for analysis and summarization.

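### Windows for PK and marker samples after the last dose are counted from Day 1, not from the actual third dose, which adds modest, avoidable scheduling noise to third-dose Cmax and tmax

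*Protocol*

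**What the plan says.** Protocol 7.2 lists acceptable windows for visits and for PK and marker samples: ± "2 days for days 8 and 64", ± "3 days for days 15, 29, 57, 71, and 85" and ± "7 days for days 113 and 169/EOS". Protocol 7.4.13.3 fixes the schedule: "Serum PK samples will be collected at days 1, 8, 15, 29, 57, 64, 71, 85, 113, and" 169/EOS. Blood on dosing days is drawn before dosing (Protocol 7.2 and 7.4.13.3).

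SAP 5.2 defines "study day= (study date - date of study Day 1) +1". SAP Appendix A uses that scale to assign PK and marker samples to visits; for example, Day 64 covers Study Days 61 to 67. Neither document relates the Day 64, 71, 85 or 113 sample to the date on which the last dose was actually given.

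For the parameters themselves, Protocol 10.4.2 and SAP 9.5.1 say: "Actual dosing and sampling times will be used for calculation of PK parameters". The protocol allows compartmental or non-compartmental estimation; the SAP specifies non-compartmental.

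The dosing days are redacted. A third dose at Day 57 is inferred from four places. Protocol Table 1 predicts exposure after three doses. Weight is taken at dosing (Protocol 6.2.1.3), and the on-treatment weight visits in SAP Appendix A are baseline, Day 29 and Day 57. Pregnancy tests on dosing days (Protocol 7.3) show the same pattern in Table 6. Follow-up starts at Day 64.

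**The concern.** The first dose fixes Day 1, so the Day 8 sample has only its own tolerance around the dose. After the third dose two tolerances combine, because the dosing visit can move one way and the sampling visit the other. Since the Day 57 blood is drawn before dosing, Day 64 is the first sample after the third dose and usually the only one near its peak. In adults, "Generally, Cmax was observed within the first week after administration". A sample at 12 days would be past that peak, and one at 2 days may come before it.

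Cmax, tmax and AUC belong to the primary endpoint, Table 1 predicts exposure after three doses, and each cohort has 4 subjects. Visit scheduling would then be mixed into the between-subject variability that the trial sets out to describe.

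**Working it through.** **Inputs.** Third dose at Day 57 ± 3, so Days 54 to 60 (day inferred, window from Protocol 7.2). Samples at Day 64 ± 2, Day 71 ± 3, Day 85 ± 3 and Day 113 ± 7. The plan states no figure for time since dose, so there is nothing to reproduce first.

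**Time since the third dose.** Shortest = (sample day − its window) − 60. Longest = (sample day + its window) − 54. If anchored to the dose, time = (sample day − 57) ± its window.

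| Sample | As written (days) | Anchored (days) |
|---|---|---|
| Day 64 | 62 − 60 = 2 to 66 − 54 = 12 | 5 to 9 |
| Day 71 | 68 − 60 = 8 to 74 − 54 = 20 | 11 to 17 |
| Day 85 | 82 − 60 = 22 to 88 − 54 = 34 | 25 to 31 |
| Day 113 | 106 − 60 = 46 to 120 − 54 = 66 | 49 to 63 |

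For comparison, Day 8 after the first dose: 6 − 1 = 5 to 10 − 1 = 9 days. The SAP Day 64 analysis window (Study Days 61 to 67) admits 61 − 60 = 1 to 67 − 54 = 13 days.

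**How often.** There are 7 possible dosing days and 5 possible Day 64 sampling days, so 35 combinations. Treated as equally likely and independent (an assumption), the counts at 2, 3, …, 12 days are 1, 2, 3, 4, 5, 5, 5, 4, 3, 2, 1. Outside 5 to 9 days: 1 + 2 + 3 + 3 + 2 + 1 = 12 of 35 (34%). At the 2- or 12-day ends: 2 of 35 (6%).

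**Effect on Cmax.** The illustration is a linear one-compartment model with first-order absorption at 0.4/day (assumed), adult half-lives from Protocol 2.2.2, and doses on Days 1, 29 and 54 to 60. Observed Cmax is the higher of the Day 64 and Day 71 samples, divided by the model's true peak, over all in-window combinations.

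| Half-life (days) | CV as written | CV anchored | Lowest ratio as written | Lowest ratio anchored |
|---|---|---|---|---|
| 11 | 7.5% | 4.5% | 0.75 | 0.88 |
| 12.8 | 6.4% | 3.7% | 0.78 | 0.90 |
| 18 | 4.4% | 2.3% | 0.83 | 0.94 |

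With the terminal-phase value of 6.5 days throughout, the CV is 13.5% as written and 8.9% anchored. In a second set of 12 scenarios (half-life 6.5, 12.8 or 18 days; time to peak 2, 3, 5 or 7 days), anchoring raised the lowest observed/true Cmax in every one.

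**Against the expected spread.** Reading Table 1's 90% intervals for Cmax as log-normal, SD = ln(upper/lower) / (2 × 1.645). This gives ln(16/5)/3.29 = 0.35, ln(65/21)/3.29 = 0.34 and ln(119/41)/3.29 = 0.32. Adding scheduling noise in quadrature to 0.34: √(0.34² + 0.04²)/0.34 = 1.007 and √(0.34² + 0.08²)/0.34 = 1.027. The total spread rises by about 1% to 3%.

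**The case against.** The strongest reply is that the effect is small. 23 of the 35 combinations already lie within 5 to 9 days, Protocol 7.2 asks sites to make every effort to follow the schedule, and the Day 71 sample can partly rescue a Cmax missed at Day 64. The added noise is minor beside the spread implied by Table 1. All of this stands, and it limits the point to an optional change.

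The larger limitation is having one sample in the first week after the dose. Even at nominal times, the 12 scenarios give observed/true Cmax of 0.63 to 1.00. Anchoring does not remove that bias. Protocol 2.5 also says that the data may enter a population PK/PD analysis, which copes with varied sampling times; that does not help the non-compartmental primary endpoint.

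The anchor is partly inferred as well. Section 7.2 does not say what its windows are counted from; the Day 1 scale comes from the SAP's study-day definition, and the dosing days are redacted.

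A reader might infer three stronger points that the documents do not support:

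- That an early Day 85 sample, at 22 days, forces extrapolation of the last 6 of 28 days. It does not, because the Day 113 sample allows interpolation.
- That the AUC interval would differ in length between subjects. On the inferred three-dose schedule no later dose cuts the profile short, so a fixed 0 to 28 day AUC can be computed on actual times, and neither document ends AUC at the Day 85 visit.
- That a third-to-first-dose accumulation ratio is distorted. No such ratio is planned; accumulation appears only as adult background in Protocol 2.2.2.

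**Conclusion.** The point holds as a modest, avoidable source of noise. Given a third dose at the Day 57 visit and windows counted from Day 1, the ranges of 2 to 12, 8 to 20 and 22 to 34 days are exact and need no protocol deviation. Actual times put each AUC point at its true time, but they cannot recover a peak that was not sampled, so Cmax and tmax remain exposed.

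The size rests on assumptions: adult half-lives, an assumed absorption rate, linear elimination without target-mediated clearance, and equally likely, independent in-window days. On those terms anchoring removes roughly 40% to 50% of the scheduling CV in Cmax at half-lives of 11 to 18 days, and about a third at 6.5 days. The finding does not undermine the primary analysis. Priority is low (could be changed), and confidence is moderate because the dosing days are redacted.

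**What to change.** In Protocol 7.2 and Table 6, define the Day 64, 71, 85 and 113 PK and marker sampling visits as 7, 14, 28 and 56 days after the actual date of the third dose, keeping the tolerances of 2, 3, 3 and 7 days. In SAP Appendix A, assign PK and marker samples taken after the third dose by days since that dose. The Day 64 sample then falls at 5 to 9 days, as Day 8 does after the first dose.

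The cost is wording in two documents. No visit, blood draw or dosing rule is added. Later visit dates move by up to 3 days for a subject whose Day 57 visit was early or late. If sampling is already complete, the SAP change alone can still be made; it would tidy the visit summaries and mean plots, but could not alter which concentrations were sampled.
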